### 3.0 LIST OF ABBREVIATIONS

%CV	percent coefficient of variation
hCG	human chorionic gonadotropin
AE	adverse event
ALT	alanine aminotransferase
AST	aspartate aminotransferase
AUC last	area under the concentration-time curve from time 0 to time of the last quantifiable concentration
AUC ∞	area under the concentration-time curve from time 0 to infinity, calculated using the observed value of the last quantifiable concentration
BLQ	below the limit of quantification
BMI	body mass index
BUN	blood urea nitrogen
CPK	creatinine phosphokinase
CFR	Code of Federal Regulations
CI	confidence interval
CL R	renal clearance
C max	maximum observed concentration
CNS	central nervous system
CRU	clinical research unit
CYP	cytochrome P-450
DA	dopamine
DNA	deoxyribonucleic acid
DDI	drug-drug interaction
ECG	electrocardiogram
eCRF	electronic case report form
EMA	European Medicines Agency
EPS	extrapyramidal symptoms
f e	fraction of administered dose of drug excreted in urine
FDA	Food and Drug Administration
FSH	follicle-stimulating hormone
GCP	Good Clinical Practice
GGT	Gamma-glutamyl transferase
GI	gastrointestinal
GM	geometric mean
HIV	human immunodeficiency virus
HR	heart rate
ICF	Informed Consent Form
ICH	International Conference on Harmonisation
IEC	independent ethics committee
IRB	institutional review board

---

LFT	liver function test
LLN	lower limit of normal
MAV	markedly abnormal value
MedDRA	Medical Dictionary for Regulatory Activities
PD	pharmacodynamics
PGx	pharmacogenomics
PK	pharmacokinetic(s)
PO	oral(ly)
PT	preferred term
QD	once daily
QTcF	QT interval with Fridericia correction method
RBC	red blood cell
RNA	ribonucleic acid
SAE	serious adverse event
SAP	statistical analysis plan
SD	standard deviation
SDB	standard database
SOC	system organ class
SUSAR	suspected unexpected serious adverse reactions
$t_{1/2}$	half-life
$t_{max}$	time of first occurrence of $C_{max}$
TEAE	treatment-emergent adverse event
TLGs	tables, listings, and graphs
ULN	upper limit of normal
WBC	white blood cell
WHODrug	World Health Organization Drug Dictionary

## 4.0 OBJECTIVES

### 4.1 Primary Objectives

The primary objective of the trial is to evaluate the effect of the potent CYP3A4 inhibitor itraconazole on the single-dose pharmacokinetics (PK) of PO TAK-906 maleate.

### 4.2 Secondary Objectives

The secondary objective of the trial to evaluate the safety and tolerability of single PO dose of TAK-906 maleate in the presence and absence of a potent CYP3A4 inhibitor.

### 4.3 Exploratory Objectives

Exploratory objectives of this trial include:

CCI

### 4.4 Study Design

This is a phase 1, single-sequence, open-label, 2-period crossover trial in approximately 12 healthy male and female (nonchildbearing-potential) subjects. The trial is designed to investigate the effect of a potent CYP3A4 inhibitor (itraconazole) on the PK of TAK-906.

The trial will include a Screening Visit, a Period 1 (Days 1 to 3), followed by a minimum of a 4-day washout from the time of TAK-906 maleate dose, a Period 2 (Days 1 to 6), and a Follow-up Visit.

On Day 1 of Period 1, eligible subjects will be enrolled into the trial and will receive a single PO dose of TAK-906 maleate 25 mg. On Days 1 to 5, inclusive, of Period 2, subjects will receive itraconazole 200 mg once daily (QD) PO solution. Following after an overnight fast of at least 8 hours, a single PO dose of TAK-906 maleate 25 mg will be administered 1 hour after the itraconazole dose on Day 4 of Period 2. Both doses of TAK-906 maleate will be administered after an overnight fast of at least 8 hours as food reduces its bioavailability by approximately 40%.

Itraconazole will be administered to subjects under clinic supervision on an outpatient basis on the morning of Days 1 to 3 of Period 2 and during confinement on Days 4 to 5 of Period 2.

Blood samples for assessment of TAK-906 concentrations will be collected from predose to 48 hours after each dose of TAK-906 maleate. Samples may be assayed for TAK-906 metabolites if deemed necessary. Urine samples will be collected through 48 hours and may be assayed for TAK-906 concentrations and metabolites if deemed necessary for the interpretation of data.

[figure not shown]
Whole blood samples for deoxyribonucleic acid (DNA) pharmacogenomics (PGx) analysis and ribonucleic acid (RNA) isolation will be collected predose on Day 1 of Trial Period 1.

Safety will be assessed by monitoring for adverse events, vital signs, ECGs, clinical laboratory results, and physical examinations throughout each dosing period.

After completion of the trial (or following subject withdrawal), all subjects will return for a Follow-up Visit 10 to 14 days after their last dose of TAK-906 maleate.

A schematic of the study design is shown in [Figure 4.a](#). A schedule of assessments is listed in [Appendix A](#).

**Figure 4.a Trial Schematic**

## 5.0 ANALYSIS ENDPOINTS

### 5.1 Primary Endpoints

The primary endpoints of the trial are the following plasma PK parameters for TAK-906 on Days 1 and 4:

- Maximum observed concentration ( $C_{max}$ ).
- Area under the concentration-time curve from time 0 to time of the last quantifiable concentration ( $AUC_{last}$ ).
- Area under the concentration-time curve from time 0 to infinity, calculated using the observed value of the last quantifiable concentration ( $AUC_{\infty}$ ).

### 5.2 Safety Endpoints

[figure not shown]
Safety endpoints include the following:

- Safety and tolerability will be assessed through physical examinations, ECGs, vital signs, clinical laboratory results, and collection of spontaneous adverse events (AEs).

### 5.3 Exploratory Endpoints

Exploratory endpoints will be assessed through the following parameters:

CCI

## 6.0 DETERMINATION OF SAMPLE SIZE

Approximately 12 subjects will be enrolled in this trial. The sample size justification is based on an acceptance range of 50% to 200% and assumes that the intrasubject %CV for  $AUC_{last}$  and  $C_{max}$  of TAK-906 will not exceed 25%. This sample size will provide 80% power to conclude plasma concentration of TAK-906 will not increase more than 2-fold in presence of itraconazole.

Subjects who drop out for nonsafety reasons may be replaced at the discretion of the investigator in consultation with the sponsor. Subjects who drop out for safety reasons will not be replaced.

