**Sample Size Justification:**

Approximately 12 subjects will be enrolled in this trial. The sample size justification is based on an acceptance range of 50% to 200% and assumes that the intrasubject percent coefficient of variation (%CV) for  $AUC_{last}$  and  $C_{max}$  of TAK-906 will not exceed 25%. This sample size will provide 80% power to conclude plasma concentration of TAK-906 will not increase more than 2-fold in the presence of itraconazole.

Subjects who drop out for nonsafety reasons may be replaced at the discretion of the investigator in consultation with the sponsor. Subjects who drop out for safety reasons will not be replaced.

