## **11.3 Determination of Sample Size**

Approximately 12 subjects will be enrolled in this trial. The sample size justification is based on an acceptance range of 50% to 200% and assumes that the intrasubject %CV for AUClast and Cmax of TAK-906 will not exceed 25%. This sample size will provide 80% power to conclude plasma concentration of TAK-906 will not increase more than 2-fold in presence of itraconazole.

Subjects who drop out for nonsafety reasons may be replaced at the discretion of the investigator in consultation with the sponsor. Subjects who drop out for safety reasons will not be replaced.

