#### *Plasma*

CCI

CCI  
[Redacted]

*Urine*

CCI  
[Redacted]

Additional plasma and/or urine PK parameters may be calculated if necessary, in accordance with the Clinical Pharmacology Analysis Plan (CPAP).

Plasma and urine PK parameters of TAK-906 and any measured metabolites will be summarized by regimen using descriptive statistics. In addition, geometric mean and %CV will be computed for  $C_{max}$  and AUCs ( $AUC_{last}$  and  $AUC_{\infty}$ ).

Box plots and scatter plots for  $C_{max}$  and AUCs ( $AUC_{last}$  and  $AUC_{\infty}$ ) will be generated by regimen.

For evaluation of potential effect of itraconazole on TAK-906 PK, paired t-tests and associated 90% confidence intervals (CIs) will be determined on the natural logarithms of  $C_{max}$  and AUCs ( $AUC_{last}$  and  $AUC_{\infty}$ ) to compare the exposure between regimens. The geometric mean of the relative bioavailability of the TAK-906 maleate with itraconazole regimen relative to the TAK-906 maleate alone regimen and the associated 90% CIs will be determined by exponentiating the appropriate estimates for the difference between regimens in the log-transformed parameters.

All PK parameters calculated will be presented in data listings.

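### Is the stated 80% power wrong, given that 12 subjects, a 25% CV and limits of 50% to 200% give almost 100% when there is no interaction?

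*SAP*

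**What the plan says.** The sample size text is the same in substance in three places: the Protocol 1.0 summary, Protocol 11.3 and SAP 6.0.

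- Size: "Approximately 12 subjects will be enrolled in this trial" (SAP 6.0).
- Limits: "The sample size justification is based on an acceptance range of 50% to 200"% (Protocol 11.3).
- Variability: the intrasubject CV for AUClast and Cmax "of TAK-906 will not exceed 25"% (SAP 6.0). This is a ceiling, not a point estimate.
- Power: "This sample size will provide 80% power to conclude plasma concentration of TAK-906 will not increase more than 2-fold in presence of itraconazole" (SAP 6.0).
- Dropouts: those leaving for other than safety reasons may be replaced; "Subjects who drop out for safety reasons will not be replaced" (SAP 6.0). Protocol 7.7 allows replacement after discontinuation in general terms.

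The analysis is in SAP 7.9.1 and Protocol 11.1.3: "paired t-tests and associated 90% confidence intervals (CIs) will be determined on the natural logarithms of" Cmax and the AUCs, back-transformed to a ratio of the combined regimen to TAK-906 alone. Neither section tests the result against 50% to 200%, and neither requires several parameters to succeed together.

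No true ratio is given for the power calculation. The sample size text does not state the alpha or say that the power is per parameter.

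**The concern.** A power figure needs a true effect. The usual default when none is given is no interaction, a ratio of 1.00. On that default the stated inputs give nearly 100%, so 80% looks like an arithmetic error or a figure taken from another calculation. The gap is too wide for rounding or choice of method: at a ratio of 1.00, 4 subjects already give 82%, and 12 subjects would need a CV of about 59% to fall to 80%.

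Two things would be at stake. The 80% is the only quantitative argument for 12 subjects, and without the ratio a reader cannot tell how large an interaction it covers. A reader might also take it to cover any true increase short of 2-fold, which no design can do, because power must fall as the true ratio nears the limit. A true increase is a live possibility: Protocol 4.2 names CYP3A4 among the enzymes possibly involved, and Protocol 6.2.1 says the dose leaves room for higher exposure.

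**Working it through.** **Inputs**

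- n = 12, each subject measured in both periods (SAP 4.4 and 6.0).
- Intrasubject CV = 25%, the stated ceiling (SAP 6.0).
- Limits 0.50 to 2.00, or ±ln 2 = ±0.6931 on the log scale (SAP 6.0).
- One-sided 5% per limit, taken from the 90% interval (SAP 7.9.1, Protocol 11.1.3).
- True ratio R: not stated, so it is varied.

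**Standard error**

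- Within-subject log SD = √ln(1 + 0.25²) = 0.2462.
- SD of a paired log difference = √2 × 0.2462 = 0.3482.
- SE of the mean log difference = 0.3482/√12 = 0.1005.
- df = 11; t(0.95) = 1.796.

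**Power**

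Power is the probability that the whole 90% interval lies within the limits. For R of 1.25 and above the lower limit contributes almost nothing, so power is P(T > 1.796), where T is noncentral t with 11 df and noncentrality (ln 2 − ln R)/0.1005. The exact two-sided integration gives the same values.

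| True ratio R | ln R | Noncentrality | Power, n = 12 |
|---|---|---|---|
| 1.00 | 0 | 6.90 | >99.9% |
| 1.25 | 0.223 | 4.68 | 99.7% |
| 1.40 | 0.336 | 3.55 | 95.3% |
| 1.50 | 0.405 | 2.86 | 85.0% |
| 1.53 | 0.425 | 2.66 | 80.3% |
| 1.60 | 0.470 | 2.22 | 66.8% |
| 1.70 | 0.531 | 1.62 | 44.9% |

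**Reproducing the plan's figure**

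Solving power = 0.80 for an increase gives R = 1.532. The stated 80% follows if a ratio of about 1.5 was assumed. Starting instead from R = 1.50, the smallest n reaching 80% is 11 (81.7%; n = 10 gives 77.8%). Twelve is one more than that minimum.

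**Sensitivity of the 80% point**

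| Change | Ratio at which power is 80% |
|---|---|
| 12 completers, CV 25% | 1.53 |
| 11 completers | 1.51 |
| 10 completers | 1.49 |
| 12 completers, CV 20% | 1.61 |
| 12 completers, CV 15% | 1.70 |
| 25% read as the CV of the paired difference | 1.66 |
| Normal approximation in place of t | 1.56 |

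Under every one of these settings, power at R = 1.00 is far above 80%. The true ratio is therefore the input that is missing; no other reading of the stated inputs accounts for the 80%.

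**The case for a change.** The strongest case for a change is that the 80% is the only number defending 12 subjects, appears three times, and cannot be checked as written. It fails for larger increases: 66.8% at 1.60 and 44.9% at 1.70. Safety dropouts are not replaced, and with 10 completers power at 1.50 drops to 77.8%, below the advertised level. AUClast and Cmax are both named, so requiring both would lower power further: 0.850² = 72% at 1.50 if they were independent, more if correlated. Stating the ratio, the alpha and the per-parameter basis would take one clause.

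Part of this stands. The ratio is missing and the sentence is less informative than it should be. The rest carries less weight:

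- The decline above 1.53 applies with the CV at its ceiling. A CV of 20% moves the 80% point to 1.61.
- Losing two subjects moves that point only from 1.53 to 1.49, and dropouts for other reasons may be replaced.
- The joint figure answers a success rule that the documents do not contain. SAP 7.9.1 reports each parameter with its own ratio and interval.
- The alpha can be recovered from the 90% interval, which stands immediately before the sample size text in the Protocol 1.0 summary.

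**Conclusion.** No change is called for. The documents leave out one input, the assumed true ratio; they do not contain a demonstrated error. With 12 completers, a CV of 25%, a 90% interval within 0.50 to 2.00 and one parameter at a time, the 80% is the power at a true ratio of about 1.53 and a minimum for every smaller increase. Since the CV is itself stated as a ceiling, reading the power as a minimum is natural. An assumed ratio of 1.50 leads to 11 subjects, so about 12 is a reasonable size.

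Adding the ratio would change neither the number of subjects nor the conduct, and the geometric mean ratios and their 90% intervals would be computed and reported in the same way. Those intervals will show directly how large an increase the data can exclude, whatever ratio was assumed at planning. That a ratio near 1.5 was in fact assumed is an inference from the arithmetic; neither document says so.

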## 7.0 METHODS OF ANALYSIS AND PRESENTATION

### 7.1 General Principles

Continuous data will be summarized using descriptive statistics, including the number of subjects, mean, standard deviation (SD), median, minimum, and maximum. The coefficient of variation (%CV) and geometric mean will be included in the summary of continuous data where indicated. Categorical data will be summarized as the number and percentage of subjects in each category.

Arithmetic means, geometric means, and medians will be presented to 1 more decimal place than the recorded data, and SDs will be presented to 2 more decimal places than the recorded data, where appropriate. Where applicable, confidence intervals about a parameter estimate will be presented using the same number of decimal places as the parameter estimate and p-values will be rounded to 3 decimal places prior to assessment of statistical significance.

All study-related raw data for enrolled subjects, including derived data, will be presented in data listings. In addition, the actual day relative to the first dose will be presented, where applicable.

All statistical analyses will be performed using the SAS System Version 9.4.

#### 7.1.1 Definition of Study Days and Baseline

Study Day 1 is defined as the date of the first dose of study drug, as recorded on the electronic case report form (eCRF) study drug administration page. Other study days are defined relative to Study Day 1, with Day 1 being Study Day 1 and Day -1 being the day prior to Study Day 1. Study days prior to the first dose of study drug will be calculated as: [date of assessment/event – date of first dose of study drug]. Study days on or after the first dose of study drug will be calculated as: [date of assessment/event – date of first dose of study drug + 1].

Unless specified otherwise, baseline is defined as the last non-missing measurement prior to the first dose of study drug.

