### 9.3 PK and PGx Samples

A portion of the DNA sample will be analyzed for the presence of allelic variants in drug metabolizing enzymes, drug transporters, or putative drug targets that may contribute to the variability in the PK of TAK-906 (Drug Metabolism Enzymes and Transporters).

As PGx is an evolving science, many genes and their functions are not yet fully understood. Future data may suggest a role of these genes in drug response, which may lead to additional hypothesis-generating exploratory research and diagnostic development on stored samples.

Samples for PK analysis will be collected as specified in the Schedule of Trial Procedures (Section 3.0). Please refer to the Laboratory Manual for information on the collection, processing, and shipment of samples to the central laboratory.

It is anticipated that the total blood volume drawn for the trial will be approximately 180 mL.

Primary specimen collection parameters are provided in [Table 9.a](#).

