##### *11.1.4.2 Clinical Laboratory Evaluation*

Baseline, postdose, and change from Baseline to postdose laboratory data will be summarized by regimen. All clinical laboratory data will be provided in the data listings.

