### 7.11.2 Clinical Laboratory Evaluations

Clinical safety laboratory tests include chemistry, hematology, urinalysis, and diagnostic screening. Refer to [Appendix A](#) for scheduled clinical laboratory test measurements and to [Appendix B](#) for the list of all clinical laboratory tests.

Descriptive statistics (N, mean, median, SD, minimum and maximum) of clinical safety laboratory variables will be summarized for baseline, post-dosing, and change from baseline at each visit. Only the scheduled measurements will be included in the summary. No inferential analysis will be performed.

Individual results for hematology and chemistry laboratory tests will be evaluated against the Takeda predefined laboratory markedly abnormal value (MAV) criteria ([Appendix C](#)). All subjects that meet the MAV criteria will be presented in a data listing. If a subject has a MAV for a particular laboratory test, all visits for that subject for that parameter will be listed. The number and percentage of subjects with at least 1 post dose markedly abnormal laboratory test result will be summarized by regimen. The mapping of the subjects with post dose results which meet the MAV criteria will be listed as a table. All post dose clinical lab results within 7 days of the last

dose, including scheduled and unscheduled measurements will be included in the MAV summaries.

All clinical laboratory data will be presented in both SI and conventional units in the data listings. Laboratory data outside of the normal reference range will be flagged on the listing along with values meeting MAV criteria.

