### 7.11.3 Vital Signs

Vital sign measurements include body temperature, pulse, respiratory rate, and blood pressure. Refer to [Appendix A](#) for scheduled vital signs measurement visits.

Descriptive statistics (N, mean, median, SD, minimum and maximum) of these vital signs will be summarized by regimen for baseline, post-dosing, and change from baseline at each scheduled time point. For each regimen (period), baseline is defined as the last non-missing vital sign measurement at or prior to predose (time relative to TAK-906 dosing) in the corresponding period. Only the vital signs collected at the scheduled visits or time points will be included in the summary. No inferential analysis will be performed for the observed vital signs.

All individual vital signs that meet Takeda's predefined criteria for markedly abnormal values ([Appendix D](#)) will be listed. The number and percentage of subjects with at least 1 post dose markedly abnormal vital sign measurement will be summarized by regimen. The mapping of the subjects with post dose results which meet the MAV criteria will be listed as a table. All post dose vital signs within 7 days of the last dose, including both scheduled and unscheduled measurements, will be included in the MAV summaries.

All vital sign data will be presented in the listings. Vital sign MAVs will be flagged in the listings.

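### SAP 7.11.2 sets no period baseline for laboratory data, so the Period 2 Day 6 change is measured from before Period 1 and shown by visit, where the protocol asks for change by regimen

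*SAP*

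**What the plan says.** **General rule.** SAP 7.1.1: "Unless specified otherwise, baseline is defined as the last non-missing measurement prior to the first dose of study drug". The same section fixes which dose that is: "Study Day 1 is defined as the date of the first dose of study drug". In this single-sequence trial it is the TAK-906 dose on Period 1 Day 1.

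**Laboratory data.** SAP 7.11.2 says that descriptive statistics "will be summarized for baseline, post-dosing, and change from baseline at each visit". It names no other baseline, so the general rule applies. The same section summarizes markedly abnormal laboratory results by regimen.

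**Vital signs and ECGs.** SAP 7.11.3 departs from the general rule: "For each regimen (period), baseline is defined as the last non-missing vital sign measurement at or prior to predose", timed relative to the TAK-906 dose in that period. SAP 7.11.4 does the same for ECGs.

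**Protocol.** Section 11.1.4 calls for safety summaries under three regimens (TAK-906 alone, itraconazole alone, the combination). Section 11.1.4.2 repeats this for laboratory data: "Baseline, postdose, and change from Baseline to postdose laboratory data will be summarized by regimen". The protocol does not define a laboratory baseline. SAP 7.13 lists no changes.

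**Schedule.** In SAP Appendix A, haematology, chemistry and urinalysis fall at Screening, Day -1, Period 2 Day 1, Period 2 Day 6 and Follow-up. Footnote (b) marks the Day -1 and Period 2 Day 1 samples as predose assessments.

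**The concern.** The schedule collects a predose laboratory sample before each period, but the SAP uses only the first as a baseline. The Period 2 Day 1 sample, drawn before any itraconazole, enters the tables only as a post-dosing visit.

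Day 6 is the only scheduled in-period laboratory sample after the combination has been given. Its change from Day -1 adds whatever happened in Period 1 and the washout to whatever happened in Period 2. A change table by regimen, as the protocol asks, also cannot be programmed from the documents as written. Neither states the baseline for the Period 2 regimens, so someone would have to choose it later, possibly with the data in view.

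At stake is how readable one descriptive table is. It supports the secondary objective, safety and tolerability with and without the inhibitor.

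**Working it through.** The plan gives no figure to reproduce here. The check rests on definitions, dates and one identity.

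**1. Interval covered by the Day 6 change.**
- Day -1 to Period 1 Day 1: 1 day.
- Period 1 Day 1 to Period 2 Day 1: at least 4 days (minimum washout, counted from the TAK-906 dose).
- Period 2 Day 1 to Day 6: 5 days.
- Under the SAP rule: 1 + 4 + 5 = at least 10 days.
- From the Period 2 Day 1 predose sample: 5 days, or up to 6 if it is drawn about 24 hours early, as footnote (b) allows.

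No maximum washout is stated. The trial summary does give an evaluation period of about 7 to 8 weeks (49 to 56 days). Taking the longest screening and follow-up, 28 + washout + 3 + 14 = 49 to 56, so the implied washout is about 4 to 11 days. At 11 days the Day 6 change would span 1 + 11 + 5 = 17 days.

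**2. What the change contains.** For each subject,

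(Day 6 − Day -1) = (Period 2 Day 1 − Day -1) + (Day 6 − Period 2 Day 1).

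The first term on the right belongs to Period 1 and the washout; the second belongs to Period 2.

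**3. What the by-visit table allows.** Both (Day 6 − Day -1) and (Period 2 Day 1 − Day -1) are tabulated. With the same subjects at both visits, the difference of the two means is the mean Period 2 change. The spread cannot be recovered:

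Var(Day 6 − Period 2 Day 1) = Var(Day 6 − Day -1) + Var(Period 2 Day 1 − Day -1) − 2 × Cov,

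and the covariance is not displayed. The median, minimum and maximum of the Period 2 change cannot be recovered from the table either.

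**4. Size of the Period 1 term.**
- *Residual TAK-906.* Half-life is about 4 hours (Protocol 4.1) and the minimum washout is 96 hours. 96 / 4 = 24 half-lives, and 2^-24 is about 6 × 10^-8. In effect no drug remains.
- *Blood draws.* Protocol 9.3 expects that "the total blood volume drawn for the trial will be approximately 180 mL"; the split by period is not available. Assume 30 to 60% is drawn before the Period 2 Day 1 sample, a blood volume of 4 to 6 L, haemoglobin of 14 g/dL and no recovery. The fall is 14 × (1 − exp(−V / blood volume)).
  - 30% (54 mL), 6 L: 0.13 g/dL.
  - 50% (90 mL), 5 L: 0.25 g/dL.
  - 60% (108 mL), 4 L: 0.37 g/dL.
- *Elapsed time.* At least 4 further days. The documents give no figure for laboratory drift.

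**5. What changing the baseline would and would not do.** The Period 1 term drops out of the Day 6 change. Period 2 blood draws stay in: at a 50% split they are another 90 mL, a dilution of about the same size. Itraconazole alone (Days 1 to 3) and the combination (from Day 4) also stay mixed, because there is no Day 4 laboratory sample.

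**The case against.** The strongest reply is that little turns on this. SAP 7.11.2 plans no inference. The Appendix C criteria for markedly abnormal values are absolute limits or multiples of the reference limits, so those counts do not depend on baseline. The table by visit already shows the Period 2 Day 1 change beside the Day 6 change, and individual values are listed. A drug-naive baseline is a reasonable choice for Follow-up, and it is the one needed for Period 2 Day 1, which serves as the value after TAK-906 alone. The separate ECG rule also has a visible source, since Protocol 9.1.10 sets an ECG baseline before each period, while no such text exists for laboratory data. All of this stands, and it limits the point to a minor one. It does not supply the SD, median and range of the Period 2 change, or the protocol's display by regimen.

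Four stronger readings are tempting and are not supported:

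- *TAK-906 from Period 1 contaminates the Day 6 result.* After 24 half-lives only a lasting laboratory effect of the dose could carry over, and the documents describe none.
- *The Day 6 result cannot be read as a Period 2 effect at all.* The mean can be obtained by subtraction if the same subjects contribute, and the listings allow the rest.
- *The SAP contradicts the protocol's baseline.* The protocol defines no laboratory baseline. The discrepancy is by visit against by regimen.
- *A Period 2 Day 1 baseline would bring laboratory data into line with vital signs and ECGs.* It would not. Their Period 2 baseline is the last value before TAK-906 on Day 4, after itraconazole has started; the laboratory one would precede all itraconazole.

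**Conclusion.** The point holds and is minor. As written, the Period 2 Day 6 laboratory change is measured from before Period 1, over at least about 10 days instead of 5 to 6. It includes any shift from elapsed time, blood draws or a lasting effect of the first dose. The change summary is by visit where Protocol 11.1.4.2 asks for by regimen, and the SAP does not record the difference.

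The interval follows from the schedule, with visits placed as in SAP Appendix A. The haemoglobin shift of about 0.13 to 0.37 g/dL is illustrative only: apart from the 180 mL, every input is assumed. It is a fall of about 0.9 to 2.7%, small against a criterion set 20% below the lower limit of normal. Markedly abnormal counts and the PK analysis are unaffected.

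The change is worth making because the sample is already collected and the present table cannot give the spread of the Period 2 change.

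**What to change.** Amend SAP 7.11.2 as follows.

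1. Define the Period 2 laboratory baseline as the last non-missing value before the first itraconazole dose (normally the Period 2 Day 1 predose sample), and summarize the Day 6 change from it.
2. Keep change from Day -1 for the Period 2 Day 1 sample, as the value after TAK-906 alone. Show it as a second display for Day 6 and Follow-up.
3. Align the display with the protocol: label Period 2 Day 1 as TAK-906 alone and Day 6 as TAK-906 with itraconazole, and say that no laboratory sample represents itraconazole alone. If the display by visit is kept instead, record it as a departure from Protocol 11.1.4.2.
4. Add a table note with two statements. The Day 6 change reflects Period 2 as a whole (itraconazole, then the combination, plus Period 2 blood draws). Its baseline differs from the Day 4 pre-TAK-906 baseline used for vital signs and ECGs.

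The cost is a few sentences in the SAP, a footnote and an extra column in the laboratory tables. No new samples, visits or data are needed.
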